10. TREATMENTS

10.1 Treatments to be Administered

Eligible subjects will be allocated in a blinded fashion to one of the three treatment groups, according to a computer-generated randomisation list.

- Group A: two tablets of Rifaximin-EIR 250 mg formulation t.i.d. (1500 mg daily) for 29 days; on Day 30 subjects will receive two tablets of Rifaximin-EIR 250 mg in single administration (500 mg daily).
- Group B: one tablet of Rifaximin-EIR 250 mg formulation t.i.d. (750 mg daily) + one tablet of placebo t.i.d. for 29 days; on Day 30 subjects will receive one tablet of Rifaximin-EIR 250 mg and one tablet of placebo in single administration (250 mg daily).
- Group C: two tablets of placebo t.i.d. for 29 days; on Day 30 subjects will receive two tablets
 of placebo in single administration.

The Investigator at each study site will be responsible for the handling and storage of the study material (in accordance with the Sponsor's indications).

Important note: Investigational products are only allowed to be administered to subjects selected for this clinical trial according to the study protocol.

10.2 Investigational Products

10.2.1 Test preparation

Rifaximin-EIR will be supplied as tablets containing 250 mg of active ingredient.

One Rifaximin-EIR 250 mg tablet (Rifaximin Delayed-Release tablet) contains:

One placebo tablet contains:

Active ingregient: none.	Active	ingred	lient:	none.
--------------------------	--------	--------	--------	-------

10.2.2 Labelling and Packaging

Test drug and matched placebo bulk manufacturing will be performed in Glatt Air Techniques Inc [name].

All clinical material will be packaged in 95-tablets bottles. Investigational drug will be provided in boxes ("Patient's kits") including the number of bottles required for a 30-days treatment period.

Each patient kit will contain two bottles characterized by labels of two different colours (white and yellow). Bottles with labels of different colours (white and yellow) can contain either tablets of Rifaximin-EIR 250 mg or tablets of placebo depending on the treatment arm. Each patient kit will contain two bottles (one white-labelled bottle and one yellow-labelled bottle) to be utilised for the 29

days of t.i.d. treatment plus one single dose to be administered on Day 30.

Glatt Air Techniques Inc., [name] will be responsible for the IMP release

10.2.3 Storage, Dispensing, Use and Disposal of the compound during and at the end of the study

An adequate amount of Patient's kits will be initially supplied to each study centre. According to the actual rate of recruitment of the centre, additional supplies will be performed.

All investigational products must be kept in a locked place with restricted access and maintained under controlled temperature conditions at $\leq 25^{\circ}$ C. Do not refrigerate.

At visits V2, each eligible subject will receive a patient's kit containing two "treatment bottles", covering the treatment necessary for 30 days of study. Treatments will be assigned according to the randomization procedure.

At visits V3, each patient will return to the Investigator all the unused and partially used investigational product and bottles contained in the treatment box assigned for the treatment.

The Investigator must not supply the investigational product to people other than the enrolled subjects or the authorized study personnel in charge of distribute it.

Under no circumstances, without written authorisation from the Sponsor, the Investigator is allowed to supply the study drug to other study centres (or Investigators working for other centres involved in the study). Similarly, the Investigator is not allowed to or will not instruct people to use or handle the investigational drug in a way different from that described in this protocol.

The investigational products should be stored safely and properly, and they must not be used after the expiry date.

The investigational products will be self-administered by the patient, following instruction provided by the Investigator or personnel authorised by the Investigator.

The final accountability records will reconcile shipment records with those of used and returned investigational product. Any discrepancy will be accounted for. All unused investigational products will be returned or destroyed locally, based on the local regulation, but return and destruction will not occur until authorised by the Sponsor.

10.3 Method of Assigning Subjects to Treatment Groups / Randomisation

A unique subject's identification number will be assigned to all subjects consenting to be enrolled in the study obtained concatenating the center number with the screening number.

A subject who fails to meet the protocol eligibility criteria will be identified as screening failure; his/her identification number will not be reallocated.

Randomisation will occur at visit V2 after all baseline procedures have been performed and eligibility for the study has been confirmed.

Participants will be randomised, on a 1:1:1 basis, to Rifaximin-EIR 250 mg three times a day (750 mg daily) for 29 consecutive days and Rifaximin-EIR 250 mg single dose on Day 30, Rifaximin-EIR 500 mg three times a day (1500 mg daily) for 29 consecutive days and Rifaximin-EIR 500 mg single dose on Day 30, or placebo for 30 consecutive days.

Blocks will be used to assure treatment balance.

Patients will be stratified at randomization based on their L-BT status (negative vs. positive) and PK sub-study participation (yes or not).

Randomization will occur throughout an IWR system integrated into the e-CRF.

At V2, the randomization system will assign an individual Patient's kit number based on a pre-defined randomisation list.

The enrolment will be competitive.

Decoding of randomization in case of emergency is described in chapter 11.4.

The subjects will be offered participation to the PK sub-study. If they agree, they will be randomized according to the relevant stratum maintaining treatment balance among groups; otherwise, they will enter the main study.

10.4 Selection of Doses in the Study

Based on the available evidence summarized in a recent meta-analysis, Rifaximin seems to be effective and safe for the treatment of intestinal dysbiosis (Gatta et al., 2017), a condition hypothesized triggering rosacea, showing a dose-response relationship in the dose-range between 800 and 1600 mg per day (Gatta, 2017).

Rifaximin-EIR 250 mg tablet will be tested in this study. Its peculiar formulation may allow a t.i.d. administration. Therefore, in the current study, we aim to test the minimum (750 mg daily) and maximum (1500 mg daily) doses that have been shown to act at pathophysiological level (e.g. SIBO eradication).

In agreement with the published studies, the duration of treatment in this study will be 29 days for both the Rifaximin-EIR 1500 mg/daily and 750 mg/daily dosages plus Rifaximin-EIR 500mg or Rifaximin-EIR mg 250 mg single dose on Day 30, respectively.

10.5 Selection and Timing of Dose for each Patient

The experimental treatment should be taken three times a day approximately 8 hours apart, in the morning, in the afternoon and in the evening, with a small amount of water, with or without food. Treatment bottles will be characterized by labels of two different colours, white and yellow.

The participant will be instructed to start the study drug intake from the morning of V2 (Day 1), immediately after randomization and preferably early in the morning (around 8:00 AM), taking one tablet from the bottle with white label and one tablet from the bottle with yellow label, as well as one tablet from the bottle of white label and one tablet from the bottle of yellow label in the afternoon (around 4:00 PM) as well as one tablet from the bottle of white label and one tablet from the bottle and one tablet from the bottle of yellow label in the afternoon (around 4:00 PM) as well as one tablet from the bottle of white label and one tablet from the bottle of yellow label in the evening (around 12:00 PM).

Bottles with labels of different colours can contain either Rifaximin-EIR 250 mg or placebo depending on the assigned treatment arm.

For the subjects included in the PK sub-study the first drug intake must be performed at the investigational site in occasion of the randomization visit (V2, Day 1), immediately after the first blood drawing (for PK analysis) and preferably early in the morning (around 8:00 AM). Also, at V3 (Day 30) subjects participating in the PK sub-study will stay overnight at the centre to complete the PK procedures.

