23. Treatment with neomycin or other low-absorbable oral antibiotics (such as marketed rifaximin) within 90 days before randomization.
24. Topical facial, inhaled or systemic corticosteroids within 30 days prior to randomization.
25. Topical facial retinoids within 30 days before randomization.
26. Systemic retinoids within 6 months before randomization. 27. Any other topical or systemic treatment for rosacea within 30 days before randomization (including also laser and pulsed light, etc.).
28. Over-the-counter intestinal or topical skin probiotics (functional food is allowed), within 30 days before randomization.
29. Any experimental treatment within 6 months prior to randomization.
30. Current swab-positive or suspected (under investigation) Covid-19 infection;
signs or symptoms: cough, sputum production, shortness of breath within the last 14 days;
or contact with people with Covid-19 infection within the last 14 days.
31. Women who are pregnant, breast-feeding or planning a pregnancy during the trial period.
32. Subjects who are investigational site staff members and their family members, site staff members otherwise supervised by the investigator, or patients who are Alfasigma's employees.

Test products	Rifaximin-EIR 250 mg tablets or placebo.
(dose and mode of administration) and reference therapy/placebo (dose and mode of administration):	 Patients will be randomly allocated into the following treatment arms: Group A: two tablets of Rifaximin-EIR 250 mg TID (1500 mg daily) for 29 days (morning, afternoon, night); on Day 30 they will receive two tablets of Rifaximin-EIR 250 mg in single administration in the morning. Group B: one tablet of Rifaximin-EIR 250 mg (750 mg daily) + one tablet of placebo TID for 29 days (morning, afternoon, night); on Day 30 they will receive one tablet of Rifaximin-EIR 250 mg and one tablet of placebo in single administration in the morning. Group C: two tablets of placebo TID for 29 days (morning, afternoon, night); on Day 30 they will receive two tablets of placebo in single administration in the morning. Group C: two tablets of placebo TID for 29 days (morning, afternoon, night); on Day 30 they will receive two tablets of placebo in single administration in the morning.

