6. OVERALL STUDY DESIGN AND PLAN

This is a randomized, double-blind, placebo controlled, phase IIa clinical trial.

As described in Section 16.1 (Determination of Sample Size), two hundred one (201) eligible subjects are planned to participate in the main study while a subgroup of minimum 18 and maximum 36 subjects are planned to participate in the PK sub-study. A maximum of 12 (minimum 6) subjects per arm is established for the PK sub-study.

At randomization visit (V2, Day 1), subjects will be 1:1:1 randomized to receiving any of the two daily doses of active treatment or placebo. TID doses of the assigned treatment will be administered from Day 1 to Day 29. On Day 30 (V3) just the first daily dose will be administered, and PK assessed.

Patients will be stratified at randomization based on their L-BT status (negative vs. positive) and PK sub-study participation (yes or not). A negative L-BT is defined as a test showing an increase ≤ 10 ppm of H₂ by 90 minutes compared to time 0.

The primary endpoint will be evaluated at end of treatment (V3, Day 30).

Subjects participating in the PK sub-study at V3 (Day 30) will stay overnight to complete the PK assessments.

Venous blood samples for PK analysis will be collected on:

- Day 1: Pre1st dose, and at 0.5, 1, 1.5, 2, 3, 4, 6, 8 hours post dosing.
- Day 30 (V3): Pre dose (single dose in the morning), and at 0.5, 1, 1.5, 2, 3, 4, 6, 8, 12, 22, 24, 30 hours post dosing. Blood sampling will continue until Day 31 as appropriate.

Details on the procedures performed with the different recruitment options are described in Section 11 (Study Procedures).

Participants will be enrolled at approximately 40 US Centers in USA.

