9.2 Plasma PK Parameters: Definitions and Rounding Specifications

Pharmacokinetic analysis of the plasma concentration-time data for rifaximin will be performed using non-compartmental methods for extravascular administration in Phoenix[®] WinNonlin[®] version 8.2 or higher. The PK parameters presented below will be estimated where appropriate and possible.

Table 8: Plasma Pharmacokinetic Parameters

Parameter	Day	Definition	Unit	DP or SF	No. of DP/SF
T _{max}	1&30	Time of maximum observed concentration	h	DP	2
C _{max}	1&30	Maximum observed concentration	mass unit/mL	SF	3
AUC _(0-tau)	1&30	Area under the curve for the dosing interval (0-8 hours), calculated by the linear trapezoidal method defined interval between doses	mass unit.h/mL	SF	3
AUC _(0-last)	30	Area under the curve from time 0 to the time of last measurable concentration, calculated by the linear trapezoidal method	mass unit.h/mL	SF	3
AUC _{0-∞}	30	Area under the curve from time 0 extrapolated to infinity, calculated as AUC _{0-last} + Ct/Lambda-z, where Ct is the last measured concentration.	mass unit.h/mL	SF	3
t _{1/2}	30	Terminal elimination half-life, calculated as Ln(2)/ Lambda-z	h	DP	2
Lambda-z	30	First order rate constant associated with the terminal (log- linear) portion of the plasma concentration vs time curve	1/h	DP	4
AR C _{max}	30	Accumulation ratio based on Day 30 C _{max} /Day 1 C _{max}	NA	DP	2
AR AUC _(0-tau)	30	Accumulation ratio based on Day 30 AUC _(0-tau) /Day 1 AUC _(0-tau)	NA	DP	2

DP=decimal places; SF=significant figures; NA=not applicable

The nominal dose will be used in the calculation of relevant PK parameters.

The imputation of non-numerical (e.g. below the limit of quantification (BLQ)) or negative values (e.g. pre-dose sampling times) reported in the input data set will be performed as follows for calculation of PK parameters:

- Day 1 pre-dose sample times will be entered as zero
- Values that are BLQ obtained prior to C_{max} will be entered as zero
- Values that are BLQ after C_{max} will be treated as missing
- Values that are measurable after at least 2 consecutive BLQ values after C_{max} will be treated as missing for the calculation of PK parameters
- Values that are reported as "No Result" or "Not Reportable" (NR), "Not Calculated" (NC) or "No Sample" (NS) etc. will generally be considered missing

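### Protocol section 10.5 gives a clock time for the third daily dose that conflicts with its own eight-hour spacing and evening timing

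*Protocol*

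**What the plan says.** Protocol 10.5 first sets the spacing: the treatment "should be taken three times a day approximately 8 hours apart, in the morning, in the afternoon and in the evening". It then gives one clock time per dose:

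- first dose: "preferably early in the morning (around 8:00 AM"
- second dose: "in the afternoon (around 4:00 PM"
- third dose: "one tablet from the bottle of yellow label in the evening (around 12:00 PM"

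The text for the 4:00 PM dose appears twice in that sentence, in garbled form.

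Elsewhere:

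- The protocol synopsis (test products) has "1500 mg daily) for 29 days (morning, afternoon, night" for the higher dose. It names the same three times of day for the other two arms and gives no clock times.
- SAP 4.1 gives a clock time for the first dose only.
- SAP 9.2, Table 8, defines AUC(0-tau) on Days 1 and 30 as "Area under the curve for the dosing interval (0-8 hours" and forms accumulation ratios as Day 30 over Day 1.
- Protocol 6 states "Participants will be enrolled at approximately 40 US Centers in USA". Protocol 10.2.3 has patients take the drug themselves, as instructed by the investigator or authorised staff.

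**The concern.** On the 12-hour clock in use at US sites, 12:00 PM is noon. Noon is not evening or night, and it comes before the 4:00 PM dose rather than eight hours after it. The clock times and the interval in section 10.5 cannot both be followed, and neither document gives another clock time for the third dose that would settle the matter.

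The section governs what participants are told to do, so it is a natural source for the subject instructions. At stake is the PK sub-study. Its 0–8 hour dosing interval fits equal eight-hour spacing. If a sub-study patient took the third dose at the literal time, the Day 1 and Day 30 profiles would no longer describe that spacing.

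**Working it through.** **1. Gaps between doses.** Inputs: the three clock times in Protocol 10.5. Each gap is the next dose time minus the current one, modulo 24 hours.

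| Reading of 12:00 PM | Dose times in order | Gaps (h) |
|---|---|---|
| Midnight | 08:00, 16:00, 24:00 | 16−8 = 8; 24−16 = 8; 32−24 = 8 |
| Noon (literal) | 08:00, 12:00, 16:00 | 12−8 = 4; 16−12 = 4; 32−16 = 16 |

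The stated eight-hour spacing is reproduced by the midnight reading and not by the literal one.

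**2. Day 1 PK profile.** Samples are pre-dose and at 0.5, 1, 1.5, 2, 3, 4, 6 and 8 hours (Protocol 14.1, SAP 9.1). With a first dose at 08:00:

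- Eight-hour spacing: the next dose is at 16:00, the 8-hour end of the window, so no second dose falls inside it.
- Literal times: a second dose comes at 12:00, that is at 4 hours. The 6- and 8-hour samples, and AUC over 0–8 hours, would then combine two doses.

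**3. Day 30 PK profile.** Only a morning dose is given on Day 30, so there is no extra dose in this window under either reading. What changes is carry-over from Day 29:

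- Eight-hour spacing: the last dose is at 24:00, so the 08:00 pre-dose sample follows a gap of 32−24 = 8 hours.
- Literal times: the last dose is at 16:00, so the gap is 32−16 = 16 hours.

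**4. Direction of the effect, if it occurred.** Day 1 AUC(0-tau) would rise and Day 30 AUC(0-tau) would fall, so the accumulation ratio would fall for both reasons. The documents give no half-life, absorption rate or lag, so the size cannot be derived from them. For illustration only, assume a one-compartment model with absorption rate ka = 1/h, lag 0–2 h and half-life 2–12 h. Concentrations are summed over 29 days of dosing plus the Day 30 dose, each dose contributing

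ka/(ka−ke) × [exp(−ke·u) − exp(−ka·u)], with ke = ln 2 / half-life and u = time since dose minus lag (u > 0).

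| Quantity | Literal times relative to eight-hour spacing |
|---|---|
| Day 1 AUC(0–8) | 1.25 to 1.69 times |
| Day 30 pre-dose concentration | 0.08 to 0.75 times |
| Day 30 AUC(0–8) | 0.72 to 0.91 times |
| AUC accumulation ratio | lower by about 35% to 50% |

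For example, at half-life 4 h and no lag, the accumulation ratio goes from 1.43 to 0.73, and 0.73/1.43 = 0.51. These figures apply only to a patient who dosed at noon and only under the assumed kinetics. They are not an estimate for this trial.

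**5. Whether it would be seen.** Compliance is a tablet count (Protocol 10.7, SAP 6.7), which carries no timing. Actual sampling times are recorded, and elapsed time runs from administration (Protocol 14.1 and 16.3.2.2, SAP 9.2), so the times of the profiled doses are needed. Neither document asks for the time of a further dose during Day 1 sampling, or of the last dose before the Day 30 pre-dose sample. The case report form is not available here and may collect them.

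**6. Other analyses.** The ANCOVA on lesion counts and the stratified CMH test on IGA success (Protocol 16.3.1, SAP 7.2) do not use dose times.

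**The case against.** The strongest reply is that this is a slip of notation that nobody would act on. Section 10.5 states the interval, calls the third dose an evening dose and lists it after the 4:00 PM dose. The synopsis says night, and the SAP interval is eight hours. A patient would have to set all of that aside to take the last-listed dose before the second. On Day 1 a noon dose would also coincide with the nominal 4-hour sample, which has a ±10 minute window and is drawn by trained clinical staff, although the documents do not say that patients stay on site between samples. Patients follow the investigator's instructions, and that text is not in the documents.

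Most of this stands. It makes noon dosing unlikely and confines any effect to a sub-study whose parameters are only summarised descriptively and whose size has no formal statistical basis (Protocol 16.1). It does not remove the contradiction, which is in an operative instruction and is corrected nowhere else.

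A reader might infer more: that patients were told to dose at noon, or that both PK days are distorted. The documents support neither. They do not show what patients were told, they contain strong cues against a noon dose, and any distortion depends on someone actually dosing then.

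**Conclusion.** Protocol 10.5 contradicts itself on the timing of the third dose, and its clock time also disagrees with the synopsis and with the SAP's dosing interval. That much is certain from the text. A clock-notation slip is the probable cause, since a midnight reading restores equal spacing. Which of the time, the interval and the wording should stand is for the sponsor to decide.

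The consequence is conditional. If a PK sub-study patient on active drug followed the literal time, the descriptive AUC(0-tau), the pre-dose level and the accumulation ratios would be affected in the direction shown. The documents give neither the kinetics nor the likely number of such patients, so no size can be attached. A few profiles could matter to a summary because groups are small: 6 to 12 per arm were planned, with the cap later raised to 19 (SAP 4.5). The co-primary efficacy conclusions are not touched. This is an internal inconsistency of minor severity, worth correcting because correction is cheap.

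**What to change.** The sponsor should reconcile the clock time, the stated interval and the evening/night wording in Protocol 10.5, remove the duplicated 4:00 PM text, and state the result in unambiguous 24-hour notation. The subject instructions should be checked against the reconciled text. No dosing time is proposed here.

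For PK sub-study patients, record the actual time of any further dose taken during Day 1 sampling and of the last dose before the Day 30 pre-dose sample, so that a departure from the assumed interval can be identified before the parameters are summarised.

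The cost is a one-line protocol correction, a check of the subject instructions and, if the case report form does not already hold them, a few dose-time entries for each sub-study patient. No analysis method changes.

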10.6 Blinding

Blinding is intended to limit the occurrence of conscious and unconscious bias in the conduct and interpretation of a clinical trial arising from the influence which the knowledge of treatment may have on the recruitment and allocation of subjects, their subsequent care, the attitudes of subjects to the treatments, the assessment of end-points, the handling of withdrawals, the exclusion of data from analysis, and so on.

In accordance with the double-blind design, both the Investigator and the patient will be unaware of the treatment being dispensed in each case. The placebo will be indistinguishable from the active substance, i.e. will have the same weight, appearance, colour, smell and flavour.

Only in case of an emergency, when knowledge of the study medication is essential for the patient's safety, the Investigator may unblind a patient's treatment assignment (see section 11.4 "Decoding of randomisation in case of emergency").

